15.2 Safety Monitoring Analyses

AEs and clinical outcomes are monitored closely in this study. To protect the safety of subjects, safety stopping rules for the protocol and individuals sites have been developed.

15.2.1 Protocol Suspension and Review

Criteria for protocol suspension and review are detailed in the CIT-06 protocol, section 6.2.1.

After the protocol is placed on hold, no additional transplants within the trial will be performed at any participating clinical site until the CIT Steering Committee and DSMB meet either in person or by conference call to review in depth the results and circumstances surrounding the islet functional failure or SAE to determine whether the trial enrollment of new subjects and conduct of additional transplants could be safely resumed.

15.2.2 Site Suspension and Review

Criteria for suspension of study enrollment and first islet infusions at individual sites are detailed in the CIT-06 protocol, section 6.2.2.

After any site is placed on hold, no additional transplants will be performed at that site until the CIT Steering Committee and DSMB meet either in person or by conference call to review in depth the results and circumstances surrounding the islet functional failure or SAE to determine whether the trial enrollment of new subjects and conduct of additional transplants could be safely resumed at that site, or whether there could be implications for the continuation of the entire proposed pilot protocol also at other affiliated sites testing the same protocol.

Statistical Analysis Plan

In all cases of PNF, subjects will be asked to temporarily continue immunosuppression to decrease the risk of sensitization that could increase the risk of poor outcome should future transplants occur. A tapering schedule will be applied until immunosuppressants are completely discontinued.

16. Works Cited

- Benjamini, Y., & Hochberg, Y. (1995). Controlling the false discovery rate: a practical and powerful approach to multiple testing. *Journal of the Royal Statistical Society. Series B (Methodological)*, 289-300.
- Emerson, S., & Fleming, T. (1989). Symmetric group sequential designs. *Biometrics*, 905-923.
- Hintze, J. (2011). *Pass 11*. Kaysville, Utah.
- Markmann, J., S, D., Huang, X., & al., e. (2003). Insulin independence following isolated islet transplantation and a single islet infusion. *Ann Surg.* , 741-749.
- Pacini, & Bergman. (1986). MINMOD: a computer program to calculate insulin sensitivity and pancreatic responsiveness from the FSIGT. *Comp Meth, and Prog in Biomed;*, 113-122.
- Rosner, B. (1995). *Fundamentals of Biostatistics: Fourth Edition*. Belmont California: Wadsworth Publishing Company.

17.1 Appendix 1 - Descriptive Statistics of Baseline Data

	Center									
	Univ of Alberta	Univ of Miami	Univ of Minnesota	Univ of Pennsylvania	Emory Univ	Northwestern Univ	UIC	UCSF	Massachusetts General Hospital	Total
Demographic Variables										
Age n mean s.d. median range										
Sex: n (%) male female total										
Race: n (%) White Black Hispanic Asian Other										
	Disease Factors									

Statistical Analysis Plan

	Center									
	Univ of Alberta	Univ of Miami	Univ of Minnesota	Univ of Pennsylvania	Emory Univ	Northwestern Univ	UIC	UCSF	Massachusetts General Hospital	Total
Insulin Req. n mean s.d. median range										
HbA1c n mean s.d. median range										
# of Severe Hypo. n mean s.d. median range										
MAGE n mean s.d. median range										
LI n										

Statistical Analysis Plan

	Center									
	Univ of Alberta	Univ of Miami	Univ of Minnesota	Univ of Pennsylvania	Emory Univ	Northwestern Univ	UIC	UCSF	Massachusetts General Hospital	Total
mean										
s.d.										
median										
range										
Clarke Score										
n										
mean										
s.d.										
median										
range										
HYPO score										
n										
mean										
s.d.										
median										
range										
β -score										
n										
mean										
s.d.										
median										
range										
C-peptide										
glucose										
Creatinine										
Ratio										

Statistical Analysis Plan

	Center									
	Univ of Alberta	Univ of Miami	Univ of Minnesota	Univ of Pennsylvania	Emory Univ	Northwestern Univ	UIC	UCSF	Massachusetts General Hospital	Total
n										
mean										
s.d.										
median										
range										
Physical Conditions										
Body Weight										
n										
mean										
s.d.										
median										
range										
Height										
n										
mean										
s.d.										
median										
range										
QOL										
SPC										
n										
mean										
s.d.										
median										
range										
SMC										

Statistical Analysis Plan

	Center									
	Univ of Alberta	Univ of Miami	Univ of Minnesota	Univ of Pennsylvania	Emory Univ	Northwestern Univ	UIC	UCSF	Massachusetts General Hospital	Total
n										
mean										
s.d.										
median										
range										
OHS										
n										
mean										
s.d.										
median										
range										
DDS										
n										
mean										
s.d.										
median										
range										
HFS										
n										
mean										
s.d.										
median										
range										

Statistical Analysis Plan

17.2 Appendix 2 - Summary Table of Adverse Events Related to the Islet transplant and Immunosuppression Therapy

	Degrees of Event Severity					
Events	Grade 1	Grade 2	Grade 3	Grade 4	Grade 5	Total
AE related to the islet transplantation (islet product or islet transplant procedure):						
AE-IIP-1						
Number (%)						
Resolved?						
Number (%)						
mean						
s.d.						
median						
min-max						
AE-IIP-2						
Number (%)						
Resolved?						
Number (%)						
mean						
s.d.						
median						
min-max						
AE-IIP-3						
Number (%)						
Resolved?						
Number (%)						
mean						

Statistical Analysis Plan

	Degrees of Event Severity					
Events	Grade 1	Grade 2	Grade 3	Grade 4	Grade 5	Total
s.d.						
median						
min-max						
AE-IIP-4						
Number (%)						
Resolved?						
Number (%)						
mean						
s.d.						
median						
min-max						
AE-IIP-5						
Number (%)						
Resolved?						
Number (%)						
mean						
s.d.						
median						
min-max						
AE related to the immunosuppression and/or infection prophylaxis:						
AE-IP-1						
Number (%)						
Resolved?						
Number (%)						

Statistical Analysis Plan

	Degrees of Event Severity					
Events	Grade 1	Grade 2	Grade 3	Grade 4	Grade 5	Total
mean						
s.d.						
median						
min-max						
AE-IP-2						
Number (%)						
Resolved?						
Number (%)						
mean						
s.d.						
median						
min-max						
AE-IP-3						
Number (%)						
Resolved?						
Number (%)						
mean						
s.d.						
median						
min-max						
AE-IP-4						
Number (%)						
Resolved?						
Number (%)						
mean						

Statistical Analysis Plan

	Degrees of Event Severity					
Events	Grade 1	Grade 2	Grade 3	Grade 4	Grade 5	Total
s.d.						
median						
min-max						
AE-IP-5						
Number (%)						
Resolved?						
Number (%)						
mean						
s.d.						
median						
min-max						
AE-IP-6						
Number (%)						
Resolved?						
Number (%)						
mean						
s.d.						
median						
min-max						
AE-IP-7						
Number (%)						
Resolved?						
Number (%)						
mean						
s.d.						

Statistical Analysis Plan

	Degrees of Event Severity					
Events	Grade 1	Grade 2	Grade 3	Grade 4	Grade 5	Total
median						
min-max						
AE-IP-8						
Number (%)						
Resolved?						
Number (%)						
mean						
s.d.						
median						
min-max						
AE-IP-9						
Number (%)						
Resolved?						
Number (%)						
mean						
s.d.						
median						
min-max						
AE-IP-10						
Number (%)						
Resolved?						
Number (%)						
mean						
s.d.						
median						

Statistical Analysis Plan

	Degrees of Event Severity					
Events	Grade 1	Grade 2	Grade 3	Grade 4	Grade 5	Total
min-max						
AE-IP-11						
Number (%)						
Resolved?						
Number (%)						
mean						
s.d.						
median						
min-max						

Statistical Analysis Plan

17.3 Appendix 3 - Adverse Events: Number Observed and Rate with Patient Identifications Grouped by Severity and Attribution

	Degrees of Event Severity					
Events	Grade 1	Grade 2	Grade 3	Grade 4	Grade 5	Total
AE related to the islet transplantation (islet product or islet transplant procedure):						
AE-IIP-1 incidences	6 (12.5%) C11+ C12 C22 C34 C63 C66					
AE-IIP-2 incidences						
AE-IIP-3 incidences						
AE-IIP-4 incidences						
AE-IIP-5 incidences						
AE related to the immunosuppression and/or infection prophylaxis:						

Statistical Analysis Plan

AE-IP-1 incidences						
AE-IP-2 incidences						
AE-IP-3 incidences						
AE-IP-4 incidences						
AE-IP-5 incidences						
AE-IP-6 incidences						
AE-IP-7 incidences						
AE-IP-8 incidences						
AE-IP-9 incidences						
AE-IP-10 incidences						

Statistical Analysis Plan

AE-IP-11 incidences						
---------------------	--	--	--	--	--	--

+ : Patient's identification, for example C11 stands for the incidence occurring on patient number 1 at Center #1

Statistical Analysis Plan

17.4 Appendix 4 - Analysis of Adverse Events at Month # Since Transplant Eligibility Confirmation

	AE related to the islet transplantation (islet product or islet transplant procedure) or immunosuppression and/or infection prophylaxis			AE not related to the islet transplantation (islet product or islet transplant procedure) or immunosuppression and/or infection prophylaxis		
All Adverse Events	# of incidences	The incidence rate per 100 person-days (λ)	The 95 % confidence interval of λ based on MLE theory	# of incidences	The incidence rate per 100 person-days (λ)	The 95 % confidence interval of λ based on MLE theory
Body System A Grade 5 Grade 4 Event 1 Event 2 ⋮ Grade 3 Event 1 Event 2 ⋮ Grade 2 Event 1 Event 2 ⋮ Grade 1 Event 1 Event 2						

Statistical Analysis Plan

⋮						
Body System B						
Grade 5						
Grade 4						
Event 1						
Event 2						
⋮						
Grade 3						
Event 1						
Event 2						
⋮						
Grade 2						
Event 1						
Event 2						
⋮						
Grade 1						
Event 1						
Event 2						
⋮						
Body System C						
Grade 5						
Grade 4						
Event 1						
Event 2						
⋮						
Grade 3						
Event 1						
Event 2						

Statistical Analysis Plan

⋮						
Grade 2						
Event 1						
Event 2						
⋮						
Grade 1						
Event 1						
Event 2						
⋮						

Statistical Analysis Plan

17.5 Appendix 5 - Identification of Adverse Events at Month # Since Transplant Eligibility Confirmation

	AE related to the islet transplantation (islet product or islet transplant procedure) or immunosuppression and/or infection prophylaxis		AE not related to the islet transplantation (islet product or islet transplant procedure) or immunosuppression and/or infection prophylaxis	
All Adverse Events	Identification of incidences	Number and percentage of patients who have had the incidence	Identification of incidences	Number and percentage of patients who have had the incidence
Body System A				
Grade 5				
Grade 4				
Event 1	C111 C112 C113* C221 C231 C232 C331 C421 C461	6 (12.5%)		
Event 2				
⋮				
Grade 3				
Event 1				
Event 2				
⋮				
Grade 2				
Event 1				
Event 2				
⋮				
Grade 1				

Statistical Analysis Plan

Event 1 Event 2 ⋮				
Body System B Grade 5 Grade 4 Event 1 Event 2 ⋮ Grade 3 Event 1 Event 2 ⋮ Grade 2 Event 1 Event 2 ⋮ Grade 1 Event 1 Event 2 ⋮				
Body System C Grade 5 Grade 4 Event 1 Event 2 ⋮				

Statistical Analysis Plan

Grade 3				
Event 1				
Event 2				
⋮				
Grade 2				
Event 1				
Event 2				
⋮				
Grade 1				
Event 1				
Event 2				
⋮				

*: C113 stands for the third incidence of Event 1 of Grade 4 in body system A that occurs in patient #1 at Center 1.

Statistical Analysis Plan

17.6 Appendix 6 - Summary of Protocol Deviations

Centers	Number of Protocol Deviations					
	PD1	PD2	PD3	PD4	PD5	Total
University of Alberta						
University of Miami						
University of Minnesota						
University of Pennsylvania						
Emory University						
Northwestern University						
University of California San Francisco						
University of Illinois Chicago						
Massachusetts General Hospital						

17.7 Appendix 7 - Summary of Excluded Subjects

Centers	Number of excluded subjects	Reason for exclusion* (n)	# of excluded / (# of excluded + # of included)
University of Alberta			
University of Miami			
University of Minnesota			
University of Pennsylvania			
Emory University			
Northwestern University			
University of California San Francisco			
University of Illinois Chicago			
Massachusetts General Hospital			

* From list of 29 possible reasons.

Statistical Analysis Plan

17.8 Appendix 8 – Analysis Templates for the Secondary Efficacy Endpoints Measured at 75±5 Days Following the First and Last Infusion

	Center									
	Univ of Alberta	Univ of Miami	Univ of Minnesota	Univ of Pennsylvania	Emory Univ	Northwestern Univ	Univ of California San Francisco	Univ of Illinois Chicago	Massachusetts General Hospital	Total
Continuous Outcomes										
Insulin Req.										
n										
mean										
s.d.										
median										
range										
95% CI of mean										
HbA1c										
n										
mean										
s.d.										
median										
range										
95% CI of mean										
MAGE										

Statistical Analysis Plan

n mean s.d. median range 95% CI of mean										
LI n mean s.d. median range 95% CI of mean										
Hypo n mean s.d. median range 95% CI of mean										
Glucose Change n mean s.d. median										

Statistical Analysis Plan

range 95% CI of mean										
β-score n mean s.d. median range 95% CI of mean										
C- pep:glucose ratio n mean s.d. median range 95% CI of mean										
AIRglu n mean s.d. median range 95% CI of mean										

Statistical Analysis Plan

SI n mean s.d. median range 95% CI of mean										
DI n mean s.d. median range 95% CI of mean										
Glucose variability n mean s.d. median range 95% CI of mean										

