2.1 Study Design

This is a prospective, single-arm, multi-center study assessing the benefit of islet transplantation in type 1 diabetic (T1D) kidney transplant recipients. The participating centers will treat a total of 24 subjects.

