8.1 Analysis of continuous outcome variables

Continuous scale variables will be displayed as mean, standard deviation, median, minimum and maximum. The Shapiro-Wilk test (Shapiro & Wilk, 1965) will be used to test the normality of this continuous variable. If the hypothesis of normally distributed data is not rejected at the 0.05 significance level, the usual normal 95% confidence interval $\bar{x} \pm t_{0.025}^{n-1} \times \frac{s_x}{\sqrt{n}}$ will be constructed

for the true mean μ . If the data are not normally distributed, the transformations

$y = f(x) = \log x, \sqrt{x}$ and $1/x$ of these variables will be examined sequentially until we fail to reject the hypothesis of normality using the Shapiro-Wilk test at the 0.05 significance level. If a transformation is identified such that normality holds then the sample mean \bar{y} and sample standard deviation s_y will be calculated for the transformed variable. The 95% confidence interval will be constructed as

$$\left[f^{-1} \left(\bar{y} - t_{0.025}^{(n-2)} \frac{s_y}{\sqrt{n}} \right), f^{-1} \left(\bar{y} + t_{0.025}^{(n-2)} \frac{s_y}{\sqrt{n}} \right) \right].$$

If these transformations fail to achieve normality, the bootstrap method will be adopted. One thousand bootstrap samples from the original data set with replacement are obtained. For each bootstrap sample, the sample mean is calculated. The 2.5 and 97.5 percentiles, $p_{0.025}$ and $p_{0.975}$, will be identified from the 1000 bootstrap sample means. The interval $[p_{0.025}, p_{0.975}]$ will be reported as the bootstrap 95% confidence interval for the true mean.

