9.2 Analysis of Baseline Data

The number of subjects who do not meet the eligibility criteria will be reported, grouped by center. The numbers will be further broken down by the reasons for exclusion. These numbers and the corresponding rates will be reported in the summary table provided in SAP Appendix 7.

Descriptive statistics of baseline data, grouped by center, will be presented in a summary table. Continuous data will be summarized by mean, standard deviation, median, minimum, and maximum. Categorical data will be presented as numbers and percentages. The template of this table is described in SAP Appendix 1. Since the number of subjects transplanted in each center is small, there will be no significance tests for the differences of the baseline data among the seven centers.

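### Section 8.1 uses n-2 instead of n-1 degrees of freedom for back-transformed means, and Appendices 8 and 9 lay out center-level confidence intervals that the rule cannot produce at n of 2 or less

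*SAP*

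**What the plan says.** SAP Section 2.1 sets the size: "The participating centers will treat a total of 24 subjects". Section 8.1 gives the only rule for an interval around a mean. It starts with a Shapiro-Wilk test: "If the hypothesis of normally distributed data is not rejected at the 0.05 significance level, the usual normal 95% confidence interval" is built, using t with n-1 degrees of freedom. If normality is rejected, the log, square root and reciprocal are tried in turn, and the limits are back-transformed from a formula containing "y} - t_{0.025}^{(n-2)} \frac{s_y}{\sqrt{n", that is, t with n-2 degrees of freedom. Last, "If these transformations fail to achieve normality, the bootstrap method will be adopted", as a percentile interval from 1,000 resamples. No minimum n is given.

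Appendix 8 is headed "17.8 Appendix 8 – Analysis Templates for the Secondary Efficacy Endpoints Measured at 75±5 Days Following the First and Last Infusion"; Appendix 9 is its one-year counterpart. Both have nine named center columns plus Total, and each continuous outcome carries an interval row, as in "LI n mean s.d. median range 95% CI of mean". Appendix 8 has 14 continuous outcomes and Appendix 9 has 10. Appendix 1 (baseline) has the same nine center columns but no interval row.

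Section 9.2 acknowledges the small centers at baseline: "Since the number of subjects transplanted in each center is small, there will be no significance tests". The same sentence counts seven centers, not nine: "there will be no significance tests for the differences of the baseline data among the seven centers". Section 3 allows subgroup analyses with as few as 6 subjects per group, using the same methods as the main analyses.

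**The concern.** There are two linked problems. The first is a formula error. The transformed branch estimates one mean and one standard deviation from a single sample, exactly as the raw branch does, so both should use n-1. Nothing in Section 8.1 explains the loss of a second degree of freedom. The error hardly matters with all 24 subjects but grows quickly as n falls.

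The second is that the templates carry the rule down to center level, where n falls that far. As laid out, the two templates contain 14 × 9 = 126 and 10 × 9 = 90 center-level interval cells for each time point reported. Many would be impossible to fill by the stated rule or too wide to tell anyone anything. A programmer working from the templates would have to choose an undocumented substitute after the data are in hand.

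**Working it through.** **The plan's own precision figure.** Section 4.1.1 gives a half-width of about 0.4 SD. With n=24, 1.96/√24 = 0.400. With SD 0.7 for HbA1c this is 0.28, and with SD 200 for LI it is 80; both match Table 4.4. The t version is 2.069/√24 = 0.422 SD.

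**Center size.** 24/9 = 2.67; 24/7 = 3.43. Actual center sizes are not given. If subjects fall at random and equally over the centers (an assumption):
- nine centers: P(n ≤ 2) = 0.492, and 9 × 0.492 = 4.4 centers, of which 9 × 0.059 = 0.5 would have no subjects;
- seven centers: P(n ≤ 2) = 0.313, and 7 × 0.313 = 2.2 centers, of which 7 × 0.025 = 0.2 would have none.

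**Degrees of freedom in the transformed branch.** The inflation is t(n-2)/t(n-1) at the 0.975 quantile:

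| n | t, n-1 df | t, n-2 df | ratio |
|---|---|---|---|
| 3 | 4.303 | 12.706 | 2.95 |
| 4 | 3.182 | 4.303 | 1.35 |
| 6 | 2.571 | 2.776 | 1.08 |
| 24 | 2.069 | 2.074 | 1.0025 |

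**n of 2 or less.** Shapiro-Wilk needs at least three values, so no branch can be selected. At n=1 there is no SD. At n=2 the transformed formula has 0 degrees of freedom, and the raw formula, if forced, gives 12.706/√2 = 8.98 SD.

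**n=3, raw branch.** 4.303/√3 = 2.48 SD. This is correct normal-theory arithmetic, but about six times the planned 0.4 SD. For HbA1c with the Table 4.4 SD of 0.7 it is ±1.74 points, against 0.422 × 0.7 = 0.30 in Total.

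**n=3, transformed branch.** 12.706 replaces 4.303, so the interval is 2.95 times too wide on the transformed scale (99.4% coverage instead of 95%, ignoring the selection by the normality test).

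**n=3, bootstrap branch.** All three draws equal the minimum with probability (1/3)³ = 3.7%, and likewise for the maximum. Both exceed 2.5%, so apart from resampling noise the interval is [minimum, maximum]. For symmetric data, ignoring selection, it covers the mean 1 - 2/8 = 75% of the time. In simulated samples that actually reach this branch, coverage is 59% to 70%.

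**How often each branch is used at n=3** (400,000 simulated samples per distribution). The LI models are lognormal with median 223. Section 11.4 gives the median, quartiles 130 and 329, and a 90th percentile of 433; the lognormal shape is an assumption. The log-SD is ln(433/223)/1.282 = 0.52 from the 90th percentile, or ln(329/130)/1.349 = 0.69 from the quartiles.

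| Distribution | raw | transformed | bootstrap |
|---|---|---|---|
| Normal | 95.0% | 0.4% | 4.6% |
| Lognormal, 0.52 | 94.2% | 2.2% | 3.5% |
| Lognormal, 0.69 | 93.6% | 3.2% | 3.2% |

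**Scale in Total (n=24).** Total stays on the raw scale in 36% (log-SD 0.52) or 18% (log-SD 0.69) of lognormal samples. A square-root-normal model fits the Section 11.4 figures better: it gives 136, 223, 331 and 447 for the quartiles and 90th percentile, whereas the 0.69 lognormal predicts a 90th percentile of 539. Under that model Total stays raw in 67% of samples.

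**The case against.** The strongest reply is that little depends on these cells. They are rows in empty templates; no sentence in Section 8.1 or Section 11 orders center-level intervals for means. Section 10.2 calls the secondary analyses descriptive, Section 5.3.3 pools the centers for the primary analysis, and an n=1 or n=2 cell would ordinarily be printed as not estimable. Section 9.2 rules out significance tests at baseline, not descriptive intervals. All of this stands and limits the importance of the point. It does not repair the n-2 formula or tell the programmer what to do with the cells.

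Three stronger readings are tempting, and the documents do not support them.

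- A reader might infer that every n=3 interval is wrong. It is not: the raw t interval is properly built and is the one used in about 94% of samples.
- A reader might infer that center and Total columns always estimate different parameters. That happens only when the columns fall in different branches. For a strongly skewed lognormal LI it would be usual, and the arithmetic and geometric means would differ by a factor of 1.14 to 1.27. Under the better-fitting square-root model, Total usually stays raw too. The SAP states no distribution.
- A reader might fear that a change of scale would show up as a false center effect. In a simulation of the full rule with the 0.69 lognormal, the n=3 interval lay wholly above Total in 0.4% of samples and wholly below in 2.2%. Intervals this wide mainly show that they carry no information.

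**Conclusion.** The point holds in a limited form. The n-2 in the transformed branch of Section 8.1 is an error at any n. Its effect is 0.25% at n=24 and 8% at the smallest Section 3 subgroup, and it becomes large only at n=3 or 4. The center-level interval cells in Appendices 8 and 9 cannot be completed by the stated rule at n of 2 or less. At n=3 they are usually valid but uninformative, and in roughly 6% of samples over-wide or reduced to the sample range. For skewed outcomes, center and Total columns may also be on different scales, depending on the distribution.

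The degrees-of-freedom ratios and the failure at n of 2 or less are exact. The expected number of affected centers (4.4 of nine, or 2.2 of seven) rests on equal random allocation, and the branch shares rest on the assumed distributions. The primary exact binomial test does not use Section 8.1, so it is not affected; means in the Total column are changed only negligibly.

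**What to change.** 1. In Section 8.1, replace n-2 with n-1 in the transformed branch.
2. In Appendices 8 and 9, report the confidence interval of the mean in the Total column only. By center, show n with the median and range, or the individual values.
3. State in Section 8.1 that the analysis scale is chosen once per variable from the pooled data and used throughout.
4. Reconcile the seven centers of Section 9.2 with the nine template columns.

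The cost is SAP and template wording; no data collection, sample size or primary analysis changes. Dropping the center intervals loses no usable information. Center intervals built from a pooled within-center SD are possible but add a common-variance assumption and are not needed.
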